Any data or information shared for dissemination will be de-identified and the confidentiality of all participants will be strictly maintained. The only persons with access to protected health information (PHI) will include study investigators, research coordinators and those approved by the MUSC IRB. All data will be secured on MUSC servers, behind firewalls, with passwords protecting entry in these systems. All PHI will be obtained and managed in accordance with the HIPAA Privacy Rule (45 CFR Parts 160 and 164).

Increased scrutiny and remote monitoring using technology and a clinical pharmacist may lead to an increased awareness and documentation of medication side effects and adverse drug events. However, we expect these to be identified and managed very early in their course, before they can induce harm to the patient requiring further health care interventions. Early identification and resolution of medication errors, side effects and adverse drug events is the primary factor that we expect to be the mediator of reduced health care encounters and costs. To ensure this is occurring in a safe manner, the DSMP will include detailed monitoring of health care encounters and clinical outcomes, including acute rejection episodes and graft function. If there are signals that the intervention is actually inducing higher rates of these incidents, then the designated

safety officer, an experienced transplant physician, has the authority to stop enrollment and/or close the study (section E3.a). We fully expect these event rates to reduce in the intervention arm, as compared to the control arm. We do, however, have a comprehensive plan to address issues if this is, in fact, not the case.

Potential Benefits of the Proposed Research to the Subjects and Others

Patients in the intervention group may have reduced incidence and burdens associated with medication safety issues. This may potentially lead to reduced health care associated encounters, visits to the clinic and/or hospital and costs. Regardless, the completion of this study will produce data that will lead to a better understanding of the incidence, severity, root cause and potential outcomes associated with medication safety issues within kidney transplant recipients. This information can be utilized to design and test different intervention strategies to reduce these events, should the proposed intervention within this study fail to demonstrate meaningful results.

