Patients randomized to the intervention cohort will be provided the same usual care as the control cohort. In addition, this cohort of participants will receive clinical pharmacist-led supplemental medication therapy monitoring and management, utilizing a smartphone-enabled mHealth application, integrated with televisits and home-based monitoring of blood pressures and glucoses (when applicable). Subjects in this cohort will be provided with a mobile device/data plan if they are not current owners of an iPhone. All will also be provided with a Bluetooth-enabled, automated, cuff-style bicep home blood pressure monitor and a Bluetooth-enabled digital home blood glucose monitor. On the mobile device, a HIPPA compliant app developed by our collaborative group will be installed that displays the patient's medication list and alerts them when it is time to take each medication, requiring them to indicate if the medication was taken for adherence tracking. Through the app, medication regimen-specific symptom surveys will be pushed to patients that ask the frequency and severity of common side effects of their medications. The intervention will include a clinical transplant pharmacist telemonitoring patient medication adherence and blood pressure/glucose readings (if applicable) weekly and scheduling telehealth visits with patients, as outlined in Table 2.

[figure not shown]
Table 2 – Televisit schedule based on patient risk and events

Risk Level	Definition	Scheduled Televisits	Triggered Televisits
High	
Meets 2 or more of the following High-Risk Criteria
 
 • <80% adherence to medications • Missed clinic visits • Blood pressure outside of 20% of goal • <80% of blood sugars within goal range • Moderate to severe side effects 	Twice Monthly	
 • Patient reported medication change or initiation • New severe medication side effect • Critical home values of blood pressures or glucoses • Any transition in care
Moderate	
 • Meets 1 of the High-Risk Criteria 	Monthly	
Low	
 • Does not meet any of the High-Risk Criteria 	None Necessary	

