Home-based monitoring of blood pressures and glucoses, using the FORACare system, will also transfer into the application and the report dashboard.(42, 43) The app will also give providers the ability to create and send surveys to the patient. The survey will populate on the patients' home screen as an alert message. The alert message will not disappear until the survey has been filled out and submitted. Survey responses get recorded in the app and are incorporated into the report dashboard. As part of this study, patients in the intervention cohort will receive medication side effect surveys during gaps in transplant clinic visits. The survey was developed using the validated Memphis Medication Side Effect Survey, coupled with our formative research demonstrating which side effects are associated with the adverse drug events that are most commonly associated with hospital readmission.(44-46) Patients will complete this survey and this data will then flow into the report dashboard for review as aggregate and trend information. Thus, this mHealth system will allow both the patient and transplant pharmacist to track signs and symptoms of medication safety issues.

3.b Method for Assigning Subjects to Treatment Groups

Whether a patient is in the intervention group or the control will be by random selection using a random number generator in simple blocks of 8.

3.c Subject Compliance Monitoring

Monitoring for compliance with medications, clinic visits, blood pressure and glucose monitoring (if applicable) is a part of the intervention in the intervention cohort. If subjects are not complying with data monitoring in the intervention cohort, they will be contacted by the study pharmacist to encourage use of the smartphone and any relevant Bluetooth-enabled devices. If this does not resolve the noncompliance, the subject will be contacted by the study PI to discuss continued involvement in the study. These data will not be monitored real-time in the usual care cohort. Compliance with study data capture will be monitored by the study coordinators, who are completely independent of the pharmacists providing the interventions. They will gather data via direct subject interview and through review of the subject's electronic medical records.

3.d Blinding of Study Intervention

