To assess for adverse drug events, the research coordinator will review patient symptomology, vital signs and laboratory values. The research coordinator will be trained by the study pharmacists in identifying medication errors and adverse drug events, determining causality and grading the severity. To ensure objectivity and consistency in recording these events across both study cohorts, a number of safeguards will be instituted. First, the study investigators will utilize the same research coordinator to record all medication errors and adverse drug events. Second, this research coordinator will be completely independent of the telehealth intervention that is being performed and will be blinded to the patient’s randomized group. Third, only the medication errors and adverse drug events recorded by this research coordinator will be

used for data analysis. Finally, these patient assessments will be followed by an independent assessment by a clinical transplant pharmacist that is not associated with delivering the study intervention. This will ensure that event rates are not biased towards a higher capture rate in the intervention cohort, which will be receiving more intense scrutiny of their medication regimens by a clinical pharmacist.

E4 Study Outcome Measurements and Ascertainment

The primary outcome measure of this study will be the incidence and severity of medication errors and adverse drug events, which will be identified, categorized and compared between the intervention and control cohorts as detailed above and in the following sections. The exploratory outcome measures of this study are to compare the incidence and severity of acute rejections, infections, graft function, graft loss and death between research cohorts and measure the association between medication safety issues and these events. Demonstrating improvements in acute rejections, infections, graft loss or death within the intervention group will provide the data needed to design a larger, multicenter study (through dissemination efforts detailed at the end of this proposal). Additional data that will be gathered includes patient surveys to capture measures of sociodemographics, health literacy, depression, social support and trust. These are important variables that may modify or confound the impact of the intervention.

Study endpoint definitions and assessment plan:

The following will be used to define and capture data and events within this study:

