1. Medication errors will be defined as documentation that a patient is taking a medication in a manner that was not intended; synonymous with the definition developed by Overhage and utilized within our previous research.(11,14).
2. Adverse drug events will be defined according to the AHRQ Patient Safety Network, in which it describes an adverse drug event as “an adverse event (i.e., injury resulting from medical care) involving medication use”.(21) The severity of the adverse drug event will be defined according to a modified version of the CTCAE developed by the National Cancer Institute and utilized in our previous research. The CTCAE is a standardized classification system developed to assess the frequency and severity of adverse events. It was originally designed for cancer patients, but is now routinely utilized across multiple patient types in clinical research.(48, 49). In both the usual care and intervention arms, a highly trained clinical research coordinator will independently interview all participants at bimonthly intervals and review their medical records to capture and record all medication errors and adverse drug events, including timing, likely cause and severity of each event. To assess for medication errors, the research coordinator will review and compare the patient’s documented medication regimen in the electronic health record (the regimen intended to be taken) to the medication regimen actually being taken by the patient, which will be assessed using the patient’s medication bottles. To assess for adverse drug events, the research coordinator will review patient symptomology, vital signs and laboratory values. Prior to the study being opened for enrollment, the research coordinator will be extensively trained by the study pharmacists in identifying medication errors and adverse drug events, determining causality and grading the severity.

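### The ADE safeguards act only on the assessor, while only intervention patients are surveyed on side effects, so equal capture is not ensured and symptomatic ADEs are liable to be over-captured in that arm

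*Combined protocol and SAP*

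**What the plan says.** The opening of E4 makes the incidence and severity of medication errors and ADEs the primary outcome, without a grade threshold. Under E4 item 2 a coordinator will "interview all participants at bimonthly intervals and review their medical records to capture and record all medication errors and adverse drug events". Patient report is one of the inputs: "To assess for adverse drug events, the research coordinator will review patient symptomology, vital signs and laboratory values" (E3 3.e).

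E3 3.e then gives the safeguards. One coordinator records all events. That coordinator is independent of the intervention and "will be blinded to the patient’s randomized group". Only that coordinator's events are analysed. A transplant pharmacist outside the intervention makes an independent assessment. The section concludes: "This will ensure that event rates are not biased towards a higher capture rate in the intervention cohort".

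Section D3 3.a describes what the intervention arm receives through the app: "medication regimen-specific symptom surveys will be pushed to patients that ask the frequency and severity of common side effects of their medications". It adds that "patients in the intervention cohort will receive medication side effect surveys during gaps in transplant clinic visits", and of each survey that "The alert message will not disappear until the survey has been filled out and submitted". The trial is open-label for patients (D2 2.e, D3 3.d). Section D2 2.f accepts that remote monitoring with a pharmacist "may lead to an increased awareness and documentation of medication side effects and adverse drug events".

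**The concern.** A blinded assessor can apply identical rules to both arms and still record more events in one of them, if patients in that arm notice more symptoms, connect them more readily with their drugs, and mention them at interview. A survey on the side effects of one's own regimen encourages exactly that, and only one arm gets it. No side-effect survey is described for controls: the additional patient surveys in E4 cover sociodemographics, health literacy, depression, social support and trust.

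Over-capture in the intervention arm would make a real reduction in ADEs look smaller and could contribute to a false negative on part of the primary outcome. F3 has no analysis that would separate fewer events from better-reported events. This path does not need the coordinator to see televisit notes or app data. It works through what the patient says.

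**Working it through.** **Safeguards against paths.**

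| Safeguard (E3 3.e) | Acts on | Acts on what the patient reports? |
|---|---|---|
| Single coordinator | Between-rater variation | No |
| Coordinator independent and blinded | Rater expectation | No |
| Only the coordinator's events analysed | Direct entry of pharmacist or app findings | No |
| Independent pharmacist assessment | Causality, grade, validity of reported events | Only after the event has been reported |

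The last row can remove a false attribution. It cannot add a true but unmentioned symptom in a control patient, so unequal reporting survives it.

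**The plan's own power figure.** F1 gives 94% power for a 33% reduction in grade 3 or higher ADEs from 87% in controls, with 52 per arm and two-sided alpha 0.05. Read as a relative reduction, the intervention rate is 0.87 × 0.67 = 0.583. With unpooled variance:

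- difference = 0.870 − 0.583 = 0.287
- standard error = √[(0.87 × 0.13 + 0.583 × 0.417)/52] = 0.0828
- power = Φ(0.287/0.0828 − 1.96) = Φ(1.51) = 93.4%

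The pooled version gives 91.9%, or 92.4% if the intervention rate is rounded to 58%. The stated figure is reproduced to within rounding and choice of formula and is not in dispute.

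**Illustration of sensitivity.** Assumption: a fraction q of intervention patients who would otherwise have no recorded ADE report one because of the surveys, and the control rate stays at 87%. Then

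- recorded intervention rate p = 0.583 + q × (1 − 0.583)
- apparent relative reduction = 1 − p/0.87
- power = sum, over all pairs of event counts, of the two binomial probabilities wherever the Pearson chi-squared statistic is at least 3.84

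F1 uses 52 per arm; 58 is 68 × 0.85 = 57.8, the number expected at 85% retention.

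| q | Recorded rate | Apparent reduction | Power, 52 per arm | Power, 58 per arm |
|---|---|---|---|---|
| 0 | 58.3% | 33% | 93% | 95% |
| 5% | 60.4% | 31% | 89% | 92% |
| 10% | 62.5% | 28% | 84% | 88% |
| 20% | 66.6% | 23% | 71% | 76% |
| 30% | 70.8% | 19% | 54% | 59% |

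Power stays above 80%, the level F1 commits to, until q is about 13% at 52 per arm or about 17% at 58.

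**Limits of the table.** The documents give no value for q. The 87% and the 33% concern grade 3 or higher events, which a symptom survey should affect least. The lower-grade events that are most exposed count in the primary outcome, but F1 gives no rates for them. The table therefore shows the direction and the sensitivity. It does not predict a loss.

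**The case against.** The strongest reply has five parts.

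1. *The assurance is narrower than it looks.* The sentence goes on to name pharmacist scrutiny as the source of extra capture, and the safeguards do address that source. D2 2.f claims only to minimise the likelihood. This is fair as to motive, but the conclusion is stated about event rates in general, and the surveys belong to the same intervention.
2. *The interview may already be structured.* G2 promises the coordinators detailed algorithms, D2 2.f promises the same frequency and method in both arms, and most of the attachments were not in the text read here. This stands. A reader might infer that interviews rest on whatever each patient volunteers, but the documents do not show that. If a common checklist exists, citing it is enough. Even so, an equal procedure does not undo unequal earlier prompting.
3. *Causality and grade are judged by the coordinator and adjudicated blind, and vital signs, laboratory values and records are also used.* This stands as a limit on size, above all for severe events. It does not restore symptoms that controls never mention.
4. *The direction is not certain.* Intervention patients whose symptoms were settled through the app may not raise them again, and open-label patients may under-report. This stands, so the effect is liable to be diluted rather than known to be.
5. *Survey frequency is not given.* This also stands. D3 3.a places the surveys between clinic visits, and nothing says that one precedes every interview. Controls are themselves asked about ADEs at six assessments.

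**Conclusion.** The concern holds in a limited form. The design reduces assessor bias. It does not ensure equal capture, because patient reporting is unblinded and prompted about side effects by the app in one arm only, and the protocol itself expects greater awareness there. Symptomatic ADEs, mainly lower-grade ones, are liable to be over-captured in the intervention arm, which would bias the ADE comparison towards no benefit.

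The size is unknown. The conclusion rests on the assumptions that prompting raises reporting and that this outweighs any under-reporting in the same arm.

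Two stronger readings are tempting and are not supported. One is that the trial loses a stated amount of power: that needs a value of q which the documents do not give, applied to severe events that are the least exposed. The other is that a null ADE result would be uninterpretable. It would be harder to interpret, but events resting on laboratory values, diagnoses or admissions would still be informative. A positive ADE result is not threatened by this path, since over-capture in the intervention arm works against it.

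**What to change.** 1. In E3 3.e and E4 item 2, state that the blinded coordinator uses the same fixed symptom checklist, with the same two-month look-back, in both arms at all six assessments (months 2, 4, 6, 8, 10 and 12). If the coordinator algorithms mentioned in G2 already contain one, cite it. Say that this equalises elicitation but not prior prompting.
2. In F3, add a sensitivity analysis limited to ADEs supported by a usual-care laboratory value, a diagnosis made outside the study televisits, or an emergency visit or hospitalisation. Exclude events supported only by intervention televisit notes, app or home-meter data, or treatment changes initiated by the study pharmacist. D3 3.a has televisits documented in the health record and the pharmacist implementing agreed plans, so accepting those as confirmation would bring in a one-arm source.
3. In E3 3.e, replace the assurance with wording that the safeguards reduce assessor bias while patient reporting remains unblinded.

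Cost: protocol wording and a few minutes per interview. Controls may report slightly more, but on the same terms as the other arm. The sensitivity analysis will have fewer events and so less precision.

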
A2 Primary Hypothesis

Hypothesis 1: Patients in the intervention arm will have significantly fewer med errors and adverse drug events, as compared to the usual care arm, at the end of the 12-month study

Hypothesis 2: The intervention arm will have significantly fewer healthcare encounters (clinic visits, ED visits and hospitalizations), leading to reduced costs, as compared to the usual care arm, at the end of the 12-month study

A3 Purpose of the Study Protocol

Due to the complexities and toxicities associated with their immunosuppressive medication regimens, kidney transplant recipients are at high-risk of developing medication safety issues which can lead to hospitalization, increased healthcare expenditures and ultimately, graft loss. Founded on preliminary information, the use of pharmacists and mHealth technology provide a promising and innovative approach to

[figure not shown]
improve medication safety in high-risk patients. The ultimate goal of this research is to demonstrate how patients, pharmacists and technology can work hand-in-hand to optimize medication-related outcomes and reduce healthcare expenditures.

B Background

B1 Prior Literature and Studies

Within kidney transplantation, despite dramatic improvements in acute rejection rates, long-term graft survival has not improved to nearly the same degree. Since 2003, there has been a 50% reduction in acute rejection rates; yet, during this same time period, the kidney allograft half-life has only increased by a modest 0.6 years.(3, 4) The most recent report from the Scientific Registry of Transplant Recipients (SRTR) demonstrates a historically low one-year acute rejection rate of <10%, with a suboptimal five-year graft survival rate of 70%.(1) Medication safety issues, which encompass both medication errors and adverse drug events, are a predominant cause of deleterious clinical outcomes in kidney transplant recipients; most notably, graft loss.

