- Determine the incidence, severity and etiologies of med errors and adverse drug events in kidney transplant recipients and compare these between the intervention and control cohorts.

C2 Secondary Aims

- Measure the total resources utilized (hospital, outpatient, staff effort) to provide care and compare these between the intervention and control cohorts.
- Measure the impact of med errors and adverse drug events on clinical outcomes, including acute rejections, infections, graft loss and death (exploratory aim)

D Study Design

D1 Overview or Design Summary

TRANSAFE Rx is a 12-month, parallel two-arm, 1:1 randomized controlled clinical trial, involving 136 participants (68 in each arm) and measuring the clinical and economic effectiveness of a pharmacist-led intervention, which utilizes an innovative mHealth application to improve medication safety and health outcomes, as compared to usual post-transplant care. The planned study design and interventions of this project were developed from the aforementioned foundational studies. These preliminary studies provided insight into interventions that were clinically effective, efficiently implementable, had a high-rate of patient acceptability and were capable of being scalable to a wide-array of patient populations. It is within this framework that the investigators have designed the TRANSAFE Rx study.

D2 Subject Selection and Withdrawal

2.a Inclusion Criteria

- 1) Kidney transplant recipient between 6 and 36 months post-transplant
- 2) At least 18 years of age
- 3) Transplant MD agrees that patient is eligible to participate

2.b Exclusion Criteria

- 1) Multi-organ recipient
- 2) Patient is incapable of:
 - a. Measuring their own blood pressure
 - b. Measuring their own glucose (if subject has diabetes)
 - c. Self-administering medications
 - d. Speaking, hearing and reading English
 - e. Utilizing the mHealth application, after training

2.c Ethical Considerations

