Based on previous studies conducted by our research collaborative, we estimate that approximately 64% of kidney transplant recipients in the control group will experience a medication error during the one year study (defined using the Overhage criteria).(1, 2) Our previous research demonstrates that pharmacist-led initiatives can reduce these medication errors by approximately 50%.(3, 4) Using these estimates, enrolling 104 participants (52 in each cohort), will provide 92% power in detecting a statistically significant difference in medication error event rates, with a two-tailed $\alpha=0.05$. We will also have 94% power (two-tailed, $\alpha=0.05$) to detect a 33% reduction in significant adverse drug events (CTCAE grade 3 or higher), given an estimated incidence rate of 87% in the control cohort and the strong association between medication errors and adverse drug events.(2, 5) From previous analyses, we expect that the control cohort will have a mean of 18.4 ± 2.6 healthcare encounters (clinic visits, acute care/ER visits and hospitalizations), during the one year study. We estimate the intervention group will see an 8% absolute reduction in total encounters, to a mean 17.0 encounters, with an estimated 33% relative reduction in the mean number of hospital readmissions (1.2 vs. 0.8, respectively).(2) Given these estimates (two-tailed, $\alpha=0.05$), enrolling 52 patients in each arm will provide 80% power to detect a statistically significant difference. It is estimated that the intervention will also produce a mean cost savings of at least \$2,489 per patient (\$7,658 in the control cohort and \$5,169 in the intervention cohort, with σ estimated at \$4,530).(2) This study is expected to have >80% power to detect a statistically significant difference in total post-transplant costs between cohorts, given these estimates.

For the exploratory outcomes of acute rejection, infections, graft function, graft loss and death, this study is not powered to detect statistically significant differences in these clinical events between groups. However, we expect to demonstrate meaningful clinical signals, particularly with a reduction in acute rejection. Our previous study demonstrated an acute rejection rate that was 1.8 times higher in patients experiencing a significant medication error (13.7% vs. 7.7%, respectively).(2) Thus, we expect an overall acute rejection rate of 12% in the control cohort and 9% in the intervention cohort,

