corresponding with a 25% relative reduction in acute rejection rates. Based on previous randomized controlled trials conducted within the study institution, we expect to maintain an 85% retention rate.(6) We will adjust our total sample-size to 136 patients (68 in each cohort) to account for dropouts, thus maintaining adequate sample-size to produce at least 80% power to detect statistically significant differences in the primary outcome measures.

F2 Interim Monitoring and Early Stopping

The safety officer and statistician will meet at the following seven pre-designated study milestones: each time 34 patients have received at least six months of study follow-up care (four meetings), once 68 patients have completed the study (one meeting), once 102 patients have completed the study (one meeting), and at study close-out. The team will also meet on an as needed basis for any unexpected serious adverse events or significant study findings. Data will be provided at these meetings by the investigators on key variables that may indicate harm, including significant medication safety events leading to hospitalization. Study patient clinical events, including hospitalizations, emergency room visits, acute rejections, life-threatening infections, graft loss and patient death will also be reviewed during these sessions. The biostatistician will evaluate confidentiality and integrity of the database, and the procedures for recording and storing confidential files. The safety officer will also review the elements of the research plan to deal with emergencies. At the conclusion of these meetings, the recommendations of the safety officer will be reviewed and the PI and co-investigators will take appropriate corrective actions as needed.

The safety officer will have the authority to halt the trial if he/she perceives that harm is occurring due to the interventions.

F3 Analysis Plan

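### Medication errors and grade ≥3 ADEs are each powered at the full two-sided 0.05 with no stated success rule; as a minor point, ADE severity goes to tests that ignore grade order

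*Combined protocol and SAP*

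**What the plan says.** **What is primary.** E4 states: "The primary outcome measure of this study will be the incidence and severity of medication errors and adverse drug events". C1 adds etiologies to the primary aim. Under A2 Primary Hypothesis, Hypothesis 1 reads: "Patients in the intervention arm will have significantly fewer med errors and adverse drug events". Hypothesis 2, under the same heading, reads: "The intervention arm will have significantly fewer healthcare encounters (clinic visits, ED visits and hospitalizations), leading to reduced costs". C2 nevertheless lists resource use as a secondary aim ("Measure the total resources utilized (hospital, outpatient, staff effort) to provide care and compare these between the intervention and control cohorts"), and E4 names encounters and costs in neither its primary nor its exploratory outcomes.

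**Power.** F1 says that 52 per arm "will provide 92% power in detecting a statistically significant difference in medication error event rates" at two-tailed 0.05. It then gives 94% power, again at two-tailed 0.05, "to detect a 33% reduction in significant adverse drug events (CTCAE grade 3 or higher"), citing "the strong association between medication errors and adverse drug events". After the dropout adjustment to 68 per arm, the aim is "to produce at least 80% power to detect statistically significant differences in the primary outcome measures", in the plural.

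**Analysis.** F1 to F5 contain no testing order, alpha split, composite, co-primary statement or multiplicity adjustment. F3 and F4 assign nominal and ordinal variables alike to Fisher's exact or Pearson's chi-squared test, and list the severity of errors and ADEs among them. Mann-Whitney is kept for non-normal continuous variables. No ordinal model is named.

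**The concern.** A reader cannot tell which results would make the trial positive. Two readings are open, and each has a consequence that the plan does not state. If a significant result on errors alone, or on grade ≥3 ADEs alone, supports the primary claim, then two tests at 0.05 give that claim an error rate above 5%. If both are needed, the error rate is safe, but the chance of success is the joint power, and F1 gives only the two marginal powers.

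The grade ≥3 cut appears only in the power calculation; F3 and F4 do not name it as the analysed endpoint. If severity is instead tabulated over several grades, Pearson and Fisher treat the grades as unordered labels. That costs power, not type I error.

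**Working it through.** **Inputs.** From F1: errors 64% in control with a 50% relative reduction, so 32%; grade ≥3 ADEs 87% with a 33% relative reduction, so 0.87 × 0.67 = 58.3%; 52 per arm; two-sided 0.05; 85% retention of 136, so 136 × 0.85 / 2 = 57.8, taken as 58 per arm. Assumed, because the documents give no figure: the correlation between the two test statistics, 0 to 0.7.

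**Step 1: reproduce F1.** Power = Φ((d − 1.96·s0)/s1), with s0 = √(2p̄(1−p̄)/n) and s1 = √((p1(1−p1)+p2(1−p2))/n).
- Errors: d = 0.32, s0 = √(2 × 0.48 × 0.52/52) = 0.0980, s1 = √((0.2304 + 0.2176)/52) = 0.0928. (0.32 − 0.192)/0.0928 = 1.38, giving 91.6% against 92% stated.
- ADEs: d = 0.287, s0 = 0.0874, s1 = 0.0828. The argument is 1.40, giving 91.9%. Unpooled variance gives 93.4%, and taking the reduced rate as 58.0% gives 93.8%, against 94% stated. An absolute 33-point drop would give 96.8%, so the reduction is relative.

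Both figures reproduce within standard variants. At 58 per arm they are 94.2% and 94.4% (pooled).

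**Step 2: either endpoint suffices.** If independent, the family-wise error is 1 − 0.95² = 9.75%. Bivariate normal calculation gives the rest.

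| Correlation | 0 | 0.3 | 0.5 | 0.7 |
|---|---|---|---|---|
| Family-wise error | 9.75% | 9.5% | 9.1% | 8.3% |

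**Step 3: both must succeed.** There is no inflation. If independent, joint power at 52 per arm is 0.916 × 0.919 = 84.2%.

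| Correlation | 0 | 0.3 | 0.5 | 0.7 |
|---|---|---|---|---|
| Joint power, 52/arm | 84.2% | 85.1% | 86.0% | 87.2% |
| Joint power, 58/arm | 89.0% | 89.5% | 90.1% | 90.9% |

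Whatever the dependence, joint power at 52 per arm lies between 0.916 + 0.919 − 1 = 83.5% and 91.6%.

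**Step 4: rules if either is to suffice (52 per arm, pooled variance).**
- Bonferroni, 0.025 each: 86.0% for errors, 86.5% for ADEs.
- Holm: 90.9% and 91.1% if independent; 89.6% and 89.8% at correlation 0.7.
- Fixed sequence, errors first: 91.6% for errors. An ADE claim needs both tests to succeed, so its chance is the joint power, 84% to 87%.

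**Step 5: severity over several grades.** The F1 effect as an odds ratio is (0.583/0.417)/(0.87/0.13) = 0.21. I simulated 20,000 trials per cell under a common odds ratio. The five control distributions of worst grade are assumed, each with 87% at grade ≥3 (3/4/6/62/25, 5/8/55/32, 13/52/30/5, 3/4/6/44/43 and 2/4/7/50/34/3%). Odds ratios other than 0.21 are also assumed.

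| Odds ratio, 58/arm | Pearson | Wilcoxon |
|---|---|---|
| 0.21 (F1 effect) | 93–96% | 99% |
| 0.4 | 44–54% | 68–74% |
| 0.5 | 25–32% | 44–50% |

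The gain is 3 to 6 points at the F1 effect. At odds ratios 0.4 to 0.5 it is roughly 20 to 25 points, with 16 to 29 across the single distributions. Under the null, neither test exceeded 5% beyond simulation error.

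**The case against.** **The inflation is conditional.** A reader might infer that the trial runs at nearly 10% type I error. The documents do not support that: no passage says that either endpoint alone wins, and the *and* in Hypothesis 1 points the other way. A reader might also count encounters and costs, which F1 powers too, and reach 1 − 0.95⁴ = 18.5%. That is not supported either: C2 calls resource use secondary and E4 leaves it out of the primary outcome. Only the A2 heading conflicts with this. What stands is that no section states the rule, and F1 gives no joint power.

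**The severity loss may not arise.** The only severity contrast that F1 quantifies is binary, grade ≥3 or not, and a two-by-two table has no order to lose. A reader might infer a large power loss from the rows at odds ratios 0.4 and 0.5. Those effects and all the grade distributions are assumptions, and at the effect the plan itself uses the loss is a few points from a test already above 90%. This objection largely stands, so the point is minor. It remains because F3 and F4 name severity among ordinal variables and do not restrict it to the grade ≥3 cut. The point is clearest for ADEs, since E4 defines no severity scale for medication errors.

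**No passage ranks errors ahead of ADEs.** This also stands. A fixed sequence is one of several valid rules, and co-primary is closer to the plan's own wording.

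**Conclusion.** The gap is a missing decision rule. F1's two power figures are sound as marginal powers. On the more natural reading, both endpoints must succeed: the error rate is controlled, and joint power is 84% to 87% at 52 per arm (89% to 91% at 58) for correlations of 0 to 0.7. That is above the 80% target but below the 92% and 94% on the page. On the other reading, family-wise error is about 8% to 10%. The strong association cited in F1 would reduce that excess without removing it. These ranges rest on F1's assumed rates and on assumed correlations. The planned sample size can carry either rule, so this should be fixed but calls for no redesign. The severity test is a minor point and applies only if more than two grades are compared.

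**What to change.** **1. Decision rule.** In E4 and F3, declare medication-error incidence and grade ≥3 ADE incidence co-primary, each at two-sided 0.05, with success requiring both, and state the joint power in F1. If either was meant to suffice, specify Holm or a fixed sequence instead. Holm needs no order and keeps about 90% to 91% for each endpoint at 52 per arm. The sequence keeps about 92% for errors but lowers the chance of an ADE claim from about 92% to 84–87%.

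Fix the rule before any comparison by arm is made for efficacy. A deadline tied to unblinding would not work here: the trial is open-label, E3 (3.c) puts ADE summaries by severity and arm into the safety reports, and H3 has a committee that includes the investigators review adverse drug events across groups.

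Make severity and etiologies supportive, and align the A2 heading with C2 on encounters and costs.

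**2. Severity (minor).** In F3 and F4, compare worst ADE grade per patient, with no ADE as the lowest category, by Wilcoxon or proportional odds. A rank test can miss a difference in which some patients move up in grade and others down, which Pearson might detect. Worst grade also ignores the number of events.

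Both changes are wording only and add no patients or data.
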